3.2.3. Summary of Withdrawals, Treatment Assignment and Other Therapy Adherence

The number of participants who withdrew early from the study is tabulated by intervention arm. The reasons for withdrawal and time to withdrawal are also summarized.

The daily therapy ePRO questionnaire completeness, intervention assignment and ETI adherence, and dornase alfa (or hypertonic saline, if Study B) and airway clearance use are summarized by intervention arm for participants who have completed study or withdrawn.

The difference between intervention arms in participants meeting adherence criteria is estimated using logistic regression methods and reported with confidence intervals accounting for randomization strata.

3.2.4. Adverse Events

All reported SAEs and AEs are coded using MedDRA and grouped by system organ class (SOC). The number of (S)AEs is summarized by each intervention arm as follows: (i) The proportion of participants with at least one (S)AE, (ii) The average number of (S)AEs per participant, and (iii) The rate of (S)AEs per participant week of follow-up. Histograms showing the frequency of the number of (S)AEs in each intervention arm are included. The incidence and rate of (S)AEs in each intervention arm is summarized by SOC and preferred term, relationship to arm, and severity. Poisson regression modeling is used to derive rate ratios and 95% confidence intervals. Rates by arm are compared using a two-sided 0.05 level test for Poisson count data. Proportions of participants with at least one (S)AE are also compared between arms with estimated differences and corresponding 95% confidence intervals by the Newcombe-Wilson method without continuity correction; p-values are from a two-sided 0.05 level Fisher's Exact test.

The number and percent of participants changing their assigned therapy due to an adverse event is summarized by intervention arm. The number and percent of participants changing their assigned therapy when directed by a physician because of an adverse event is also summarized.

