14.4 Analysis of Safety Endpoints

All reported SAEs and AEs will be coded using MedDRA and grouped by body system. SAEs and AEs will be tabulated by treatment arm using standard coding terms sorted by body system. The incidence of AEs in each treatment arm will be tabulated by seriousness, severity, and relationship to treatment arm assignment. If an AE is reported more than once during the study period for a given subject, the greatest severity and the worst-case relationship will be presented in tables.

The number of SAEs and AEs will be summarized for each treatment arm as follows: (i) The proportion of subjects with at least one (S)AE, (ii) The average number of (S)AEs per subject, and (iii) The rate of (S)AEs per subject week of follow-up. Histograms showing the frequency of the number of (S)AEs in each treatment group will be included. Rates of (S)AEs by System Organ Class (SOC) will be presented by treatment group. Poisson regression modeling will be used to derive rate ratios and 95% CIs for each SOC. The rate ratios will be compared using a two-sided 0.05 level test for Poisson count data.

In addition to AEs, the proportion of subjects temporarily or permanently changing their assigned therapy will be summarized.

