3.2.8. Exacerbation and Concomitant Medication Parameters

The number of protocol-defined and physician identified pulmonary exacerbations (PEX) experienced by participants from Week 0 (Visit 1) to Week 6 (Visit 3) are summarized by intervention arm as follows: (i) The total number of PEX, (ii) The rate of PEX per participant week of follow-up, (iii) The average number of PEX per participant, (iv) The proportion of participants with at least one PEX, and (v) the total requiring antibiotics (acute IV, oral, or inhaled) or hospitalization. Poisson regression modeling is used to derive rate ratios and 95% confidence intervals. Rates by arm are compared using a two-sided 0.05 level test for Poisson count data. Proportions of participants with at least pulmonary exacerbation are also compared between arms with estimated differences and corresponding 95% confidence intervals by the Newcombe-

Wilson method without continuity correction; p-values are from a two-sided 0.05 level Fisher's Exact test.

Also summarized is the frequency of signs and symptoms for protocol-defined PEx for each intervention arm and overall. The difference between intervention arms in participants experiencing a protocol-defined PEx is estimated using logistic regression methods and reported with confidence intervals accounting for randomization strata.

The difference between intervention arms in participants initiating acute antibiotics is estimated using logistic regression methods and reported with confidence intervals accounting for randomization strata.

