The total number of adverse events (AEs) is presented in this table. All events occurring from randomization (Visit 1) through the end of follow-up are included. The rate of occurrence is equal to the number of events divided by the total number of follow-up weeks in each intervention arm. This table includes both serious and non-serious adverse events.

	STOP Taking (N=x)	KEEP Taking (N=x)	P-value [Final Report Only]
Total number of AEs			
AE rate [1]		Rate Ratio (95% CI)[2]	P-value[2]
Avg. Number of AEs per person			
Number (%) of Participants with at least one AE		Difference (95% CI)[3]	P-value[4]

[1] The total number of follow-up weeks in STOP taking intervention arm is X and in KEEP taking intervention arm is X.

[2] Poisson regression is used to calculate the rate ratio, corresponding 95% CI and p-value. The ratio is STOP Taking / KEEP Taking.

[3] 95% confidence interval calculated using the Newcombe-Wilson method without continuity correction. The difference is STOP Taking – KEEP Taking.

[4] The p-value is obtained from the Fisher's exact test. Included in Final Report only.

Figure 4.3. Number of Adverse Events per Participant by Intervention Arm (ITT population)

The number of adverse events per participant is displayed in the histogram below for each intervention arm. The numbers at the top of the bars indicate the number of participants that experienced the given number of adverse events.

Figure 4.4. Incidence of Adverse Events by System Organ Class (ITT population)

The left panel shows the proportion of participants experiencing at least one AE for each System Organ Class (SOC) by intervention arm. The right panel shows the difference in proportions including the 95% Newcombe-Wilson confidence interval (CI). The panels are sorted by the difference in proportions between intervention arms such that SOCs with AEs occurring more frequently in the stop taking arm as compared to the keep taking arm are listed higher.

Table 4.7. Incidence of Adverse Events (ITT population)

This table summarizes the incidence of all adverse events by the investigator. The rate of occurrence is equal to the number of events divided by the total number of follow-up weeks in each intervention arm. This table includes both serious and non-serious adverse events.

SYSTEM ORGAN CLASS	Preferred Term	STOP Taking (N=x)				KEEP Taking (N=x)				Rate Ratio (95% CI)[2]
		Participants		Events		Participants		Events		
		n	%	n	Rate[1]	n	%	n	Rate[1]	

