Number (%) of participants with at least one Respiratory AE		Prop. Diff (95% CI) [3]
FEV ₁ (% predicted) >=90 to <100%, n (%)		
Total follow-up (weeks)		
Total number of Respiratory AEs		
Respiratory AE rate [1]		Rate Ratio (95% CI) [2]
Avg. number of Respiratory AEs per person		
Number (%) of participants with at least one Respiratory AE		Prop. Diff (95% CI) [3]
FEV ₁ (% predicted) >=100%, n (%)		
Total follow-up (weeks)		
Total number of Respiratory AEs		
Respiratory AE rate [1]		Rate Ratio (95% CI) [2]
Avg. number of Respiratory AEs per person		
Number (%) of participants with at least one Respiratory AE		Prop. Diff (95% CI) [3]

[1] The rate of occurrence is equal to the number of events divided by the total number of follow-up weeks in each intervention arm for the corresponding FEV₁ (% predicted) subgroup.

[2] Poisson regression is used to calculate the rate ratio and corresponding 95% CI. The ratio is STOP Taking / KEEP Taking.

[3] 95% confidence interval calculated using the Newcombe-Wilson method without continuity correction. The difference is STOP Taking - KEEP Taking.

5 Hospitalizations and Pulmonary Function Decline

Table 5.1. Overview of Hospitalizations (ITT population)

This table presents the number of participants hospitalized, number of hospitalization events, and the number of days hospitalized between Week 0 (Visit 1) and the end of follow-up.

	STOP Taking (N=)	KEEP Taking (N=)	Total (N=)	P-value [Final Report only]
Hospitalizations Events				
Number of Hospitalization Events per Patient: N (%)				
At least one				Difference (95% CI) [2] p-value [2]
0				
1				
2				
3				
Total Number of Hospital Events				
Mean number of Events/Participant				
Rate per Week [1]				Rate Ratio (95% CI) [3] p-value [3]
Hospitalization Days				
Mean Number of Days Hospitalized per Patient (SD)				
				Rate Ratio (95% CI) [3] p-value [3]
Median				
Min, Max				

[1] The rate per week is calculated as the total number of hospitalization events divided by the total weeks of follow up for each intervention arm. The total number of follow-up weeks in STOP taking intervention arm is X and in KEEP taking intervention arm is X.

[2] 95% confidence interval for the difference in proportions is calculated using the Newcombe-Wilson method without continuity correction. The p-value is obtained from the Fisher's exact test. The difference is STOP Taking – KEEP Taking.

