- [5] Compared to reference level, one therapy at Week -2 (Screening).
- [6] Compared to reference level, no prior study enrollment.
- [7] Compared to reference level, age <18 years at Week 0 (Visit 1).
- [8] Two-sided test of null hypothesis of no difference

8 Exacerbation and Concomitant Medication Parameters

Table 8.1. Distribution of Antibiotic Use and Protocol-Defined Pulmonary Exacerbations (ITT population)

This table displays the distribution of protocol-defined pulmonary exacerbations (PEX) experienced by the participants from Week 0 (Visit 1) to Week 6 (Visit 3).

	STOP Taking (N=)	KEEP Taking (N=)	Difference (95% CI)	p-value [Final Report Only]
Total Number of Pulmonary Exacerbations [1] Rate of PEX per week of follow-up [2] Average number of PEX per participant			Rate Ratio (95% CI) [5]	p-value[5]
Distribution of Exacerbations, n (%) [1] 0 1 2				
Total no. patients with at least one Pulmonary Exacerbation, n (%)			Difference (95% CI) [6]	p-value[7]
Requiring IV Abx, n (%) [3] Requiring Oral Abx, n (%) [3, 4] Requiring Inhaled Abx, n (%) [3] Requiring Hospitalization, n (%) [3]				

[1] Protocol-Defined PEX. Exacerbations are counted as unique if their first prescription dates occur greater than 20 days apart. Protocol-defined PEX is determined by using Fuchs criteria]: clinical need for antibiotics as indicated by presence of at least 4 of 12 possible signs or symptoms listed below:

- Change in sputum volume or color
- New or increased hemoptysis
- Increased cough
- Increased dyspnea
- Increased malaise, fatigue or lethargy
- Temperature over 38°C
- Anorexia or weight loss
- Sinus pain or tenderness
- Change in sinus discharge
- Change in physical findings on examination of the chest
- Decrease in pulmonary function by 10% or more
- Radiographic changes.

[2] The total number of follow-up weeks in the STOP Taking group is X and in the KEEP Taking group is X.

[3] Percentages are based on total number of patients with at least one pulmonary exacerbation.

[4] Includes g-tube.

[5] Quasi-Poisson regression is used to calculate the rate ratio, 95% CI and corresponding p-values. The ratio is STOP Taking / KEEP Taking.

[6] The 95% confidence interval for difference in proportions is calculated using the Newcombe-Wilson method without continuity correction. The difference is STOP Taking – KEEP Taking.

[7] The p-value is based on the Fisher Exact test. Included in Final Report only.

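### AE rates are compared with plain Poisson regression although one participant can have several events; if counts are overdispersed, the overall and possibly the respiratory AE intervals are too narrow

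*SAP*

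**What the plan says.** For adverse events, SAP 3.2.4 takes the rate as all events per participant-week, derives rate ratios and 95% intervals by Poisson regression, and adds: "Rates by arm are compared using a two-sided 0.05 level test for Poisson count data". Protocol 14.4 has the matching sentence: "The rate ratios will be compared using a two-sided 0.05 level test for Poisson count data". Footnote 2 of Table 4.6 (all AEs) reads "Poisson regression is used to calculate the rate ratio, corresponding 95% CI and p-value", and footnote 2 of Table 4.11 (respiratory AEs) reads "Poisson regression is used to calculate the rate ratio and corresponding 95% CI". Tables 4.7 and 4.8 (by term and by relatedness) also use Poisson intervals. None of these places mentions a dispersion parameter, a robust variance or a negative binomial model.

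The plan expects repeat events: "Histograms showing the frequency of the number of (S)AEs in each intervention arm are included". It also has an analysis that counts each person once: "Proportions of participants with at least one (S)AE are also compared between arms with estimated differences", with Newcombe-Wilson intervals and Fisher's exact test.

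For pulmonary exacerbations the SAP gives two different models. Section 3.2.8 says "Poisson regression modeling is used to derive rate ratios and 95% confidence intervals", while footnote 5 of Tables 8.1 and 8.2 says "Quasi-Poisson regression is used to calculate the rate ratio, 95% CI and corresponding p-values".

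**The concern.** A Poisson model sets the variance of each participant's count equal to its mean. AE counts need not behave that way. Protocol 10.1 defines an AE as any unfavorable sign, symptom or disease, so one illness can produce several records. The participants also range widely in age and lung function. Differences in individual rates push the variance above the mean. The standard error from plain Poisson regression does not allow for this.

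The only dispersion correction in the SAP is in the exacerbation tables. There, counting an event as new only if it starts more than 20 days after the last leaves little room for repeats.

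AE incidence is a stated safety endpoint (Protocol 5.2). An interval that is too narrow can mislead in both directions. It can suggest a safety signal that is not there, or make the upper bound on harm from stopping look more reassuring than it is. The p-value column of Table 4.6 is restricted to the final report, but the rate-ratio interval is not, so the interval can also reach the interim safety reviews.

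**Working it through.** **The plan's own figures.** The documents give no AE rate, dispersion or precision to reproduce. Their one computed result, power of 88% and 74% for the primary endpoint (308 participants, SD 8.4, margin -3, one-sided 0.025), reproduces as 0.880 and 0.743. It does not bear on this point.

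**Inputs from the documents.** About 200 per arm, allocated 1:1 (Protocol 6.1); 6 weeks of follow-up; two-sided level 0.05 (SAP 3.2.4); about 5% starting acute antibiotics for respiratory symptoms (SAP 2.4), used as a proxy for exacerbation frequency.

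**Assumptions.** The mean AE count m per participant, and a heterogeneity parameter k (gamma-distributed individual rates). Then φ = variance/mean = 1 + m·k.

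**Effect of φ.** The correct standard error of the log rate ratio is √φ times the Poisson one. So:

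- true level = 2·[1 − Φ(1.96/√φ)]
- true coverage = 1 − true level
- correct interval width on the log scale = √φ × planned width

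| φ | 1.96/√φ | true level | coverage | width factor |
|---|---|---|---|---|
| 1.0 | 1.960 | 5.0% | 95% | 1.00 |
| 1.1 | 1.869 | 6.2% | 94% | 1.05 |
| 1.3 | 1.719 | 8.6% | 91% | 1.14 |
| 1.5 | 1.600 | 11.0% | 89% | 1.22 |
| 2.0 | 1.386 | 16.6% | 83% | 1.41 |

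**On the rate-ratio scale.** Take m = 1, which gives 200 events per arm. The Poisson standard error is √(1/200 + 1/200) = 0.100, so the interval is the estimate multiplied and divided by exp(0.196) = 1.22. At φ = 2 (k = 1) the factor should be exp(0.196 × 1.414) = 1.32.

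**Simulation, all AEs** (200 per arm, no true difference, 20,000 runs per setting). With m from 0.3 to 1.5 and k from 0.5 to 1.0 (φ from 1.15 to 2.5), plain Poisson rejects 6.4% to 21.4% of the time and quasi-Poisson 4.7% to 5.1%. With k = 0, plain Poisson holds its level at about 5%.

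**SAEs.** With an assumed m of 0.02 to 0.05, φ is 1.01 to 1.05 and the simulated Poisson level stays below 5%. At k = 1, the estimated dispersion in such sparse data falls below 1 in about 42% (m = 0.05) to 85% (m = 0.02) of runs. An unrestricted quasi-Poisson model would then narrow the interval.

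**Exacerbations.** Let 5% have at least one, and let a share q of those have a second. The mean is 0.05(1 + q) and the mean square is 0.05(1 + 3q). At q = 0, φ = (0.05 − 0.0025)/0.05 = 0.95. At q = 0.10, φ = (0.065 − 0.003025)/0.055 = 1.13. The simulated Poisson level is 3.7% to 5.9%, so the correction matters little there. At q = 0.20, φ is 1.27 and the level 7.1%.

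**The case against.** The strongest objection is that nothing in the documents shows overdispersion. Participants must be clinically stable at screening and at randomization, and are followed for only six weeks. A low AE mean with φ near 1 is plausible, and the loss is then slight (6.2% at φ = 1.1). This stands. A reader might infer that the planned intervals are certainly too narrow, but the documents support only the conditional statement.

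Second, a reader might extend the point to every rate table. That does not hold. SAE rows are too sparse to be affected. Hospitalization events and sparse system-organ-class or preferred-term rows probably behave in the same way. Among the AE tables, only 4.1 and 4.6 show a p-value for a rate ratio. Since 4.1 concerns SAEs, the inflated test is in practice the one in Table 4.6; elsewhere the effect is on intervals.

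Third, the Newcombe-Wilson and Fisher comparison is already planned, is not affected by repeat events, and directly addresses incidence. This stands and lowers the stakes. It answers a different question, however, and does not repair the reported rate ratio.

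Fourth, a reader might infer that the authors knowingly corrected exacerbations and left AEs out, or that AEs are where clustering is worst. Neither is supported. The text and footnotes on exacerbations disagree, which looks like a drafting inconsistency. Days in hospital (Table 5.1, also Poisson) could be far more dispersed: with an assumed 2% to 5% hospitalized for 5 to 14 days, φ = days × (1 − proportion) runs from 4.75 to 13.72. That count is a separate matter from this point.

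Finally, these are safety summaries without multiplicity adjustment (SAP 2.3), so the set of intervals carries no overall 5% guarantee. That limits the weight of the point, but each interval should still have its stated coverage.

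**Conclusion.** The point holds in conditional form. SAP 3.2.4, Tables 4.6 to 4.8 and 4.11, and Protocol 14.4 apply plain Poisson regression to counts that include repeat events. If the variance/mean ratio exceeds 1, the rate-ratio intervals under-cover and the Table 4.6 test is too liberal. The size ranges from no effect at a ratio of 1.0 to a true level of 16.6% and coverage of about 83% at 2.0. That range is an assumption, because the documents give neither an AE rate nor a dispersion.

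The consequence falls mainly on the overall AE rate ratio and possibly on the respiratory one. The participant-level comparison and the primary non-inferiority result are untouched. Separately, and whatever the dispersion of AE counts, SAP 3.2.8 conflicts with the footnotes of Tables 8.1 and 8.2. This is an inexpensive improvement to the safety analysis and does not threaten the trial's main conclusion.

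**What to change.** - **Overall and respiratory AE rate ratios (Tables 4.6 and 4.11) and the non-sparse rows of Tables 4.7 and 4.8:** specify quasi-Poisson or negative binomial regression, with one record per participant and log follow-up weeks as offset. State that an estimated dispersion below 1 is set to 1, so that it cannot narrow the interval.
- **SAE rows and other sparse rows:** keep Poisson and rely on the participant-level difference. State in advance the event count below which a row is treated as sparse.
- **SAP 3.2.4:** amend the wording to match, and record it as a modification of Protocol 14.4, which Protocol 14.1 allows the SAP to make.
- **SAP 3.2.8 and the footnotes of Tables 8.1 and 8.2:** reconcile them so that one model is named for exacerbation rates.

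The cost is SAP wording and one option in the model code. AE intervals become somewhat wider: 14% on the log scale at φ = 1.3 and 41% at φ = 2.0. If the dispersion is near 1, the results barely change.

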5.2 Secondary Endpoints

Secondary endpoints in each study include:

Efficacy

- Change in LCI from Visit 1 (randomization) to Visit 3 (week 6)
- Change in FEV₁ % predicted from Visit 1 (randomization) to Visit 2 (week 2)
- Proportion of subjects initiating acute antibiotics from Visit 1 (randomization) to Visit 3 (week 6)
- Proportion of subjects hospitalized from Visit 1 (randomization) to Visit 3 (week 6)
- Proportion of subjects with a pulmonary exacerbation from Visit 1 (randomization) to Visit 3 (week 6)
- Change in Chronic Respiratory Infection Symptom Score (CRISS) from Visit 1 (randomization) to Visit 3 (week 6)

- Change in the Cystic Fibrosis Questionnaire-Revised (CFQR) Respiratory Domain from Visit 1 (randomization) to Visit 3 (week 6)
- Change in FEV₁ % predicted from Screening to Visit 1 (randomization)

Safety

- Incidence of adverse events occurring between Visit 1 (randomization) to Visit 3 (week 6)
- Proportion of subjects temporarily or permanently changing their assigned therapy regimen between Visit 1 (randomization) to Visit 3 (week 6)

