11 DISCONTINUATION AND REPLACEMENT OF SUBJECTS

11.1 Early Withdrawal of Subjects from a Study

All subjects are free to withdraw from participation at any time, for any reason, specified or unspecified, and without prejudice.

Reasonable attempts will be made by the investigator to provide a reason for early subject withdrawals. The reason for the subject's early withdrawal from the study will be specified in the subject's source documents. Subjects who withdraw early from the study (prior to Visit 3) should be encouraged to come in for a final early study withdrawal visit (and the procedures to be followed would include those at Visit 3).

Subjects who for any reason modify their hypertonic saline or dornase alfa treatment such that it deviates from their assigned treatment regimen within a study will not be withdrawn from the study and are encouraged to complete all scheduled study visits.

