This table summarizes the proportion of participants changing their assigned therapy regimen (i.e., participants restarting hypertonic saline therapy in 'stop taking' arm and participants stopping hypertonic saline therapy in 'keep taking' arm) due to an adverse event (AE). Also summarized are those that were physician directed to change their assigned therapy regimen.

	STOP Taking (N=x)	KEEP Taking (N=x)	Difference in proportions (95% CI)[1]	P-value [2][Final Report Only]
Total number of AEs				
Total number (%) of AEs requiring modification				
Number (%) of Participants changing therapy regimen due to AE			Difference (95% CI)	P-value
Total number (%) of AEs requiring modification as directed by physician				
Number (%) of Participants changing therapy regimen as directed by physician due to AE			Difference (95% CI)	P-value

[1] 95% confidence interval calculated using the Newcombe-Wilson method without continuity correction. The difference is STOP Taking – KEEP Taking.

[2] The p-value is obtained from the Fisher's exact test. Included in Final Report only.

Table 4.11. Respiratory Adverse Event Overview (ITT population)

The total number of adverse events within the respiratory, thoracic and mediastinal disorders system organ class (Respiratory AEs) is presented in this table overall and by FEV1 (% predicted) category at Week 0 (Visit 1). All events occurring from randomization (Visit 1) through the end of follow-up are included. This table includes both serious and non-serious adverse events within the respiratory, thoracic and mediastinal disorders system organ class.

	STOP Taking (N=x)	KEEP Taking (N=x)	
All Participants, n (%)			
Total follow-up (weeks)			
Total number of Respiratory AEs			
Respiratory AE rate [1]			Rate Ratio (95% CI) [2]
Avg. number of Respiratory AEs per person			
Number (%) of participants with at least one Respiratory AE			Prop. Diff (95% CI) [3]
FEV ₁ (% predicted) <70%, n (%)			
Total follow-up (weeks)			

	STOP Taking (N=x)	KEEP Taking (N=x)
Total number of Respiratory AEs		
Respiratory AE rate [1]		Rate Ratio (95% CI) [2]
Avg. number of Respiratory AEs per person		
Number (%) of participants with at least one Respiratory AE		Prop. Diff (95% CI) [3]
FEV ₁ (% predicted) >=70 to <90%, n (%)		
Total follow-up (weeks)		
Total number of Respiratory AEs		
Respiratory AE rate [1]		Rate Ratio (95% CI) [2]
Avg. number of Respiratory AEs per person		

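### The SAP counts only adverse-event-driven changes of assigned therapy, so no exhibit reports the protocol's any-reason safety endpoint by arm

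*SAP*

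**What the plan says.** Protocol 5.2 lists under Safety: "Proportion of subjects temporarily or permanently changing their assigned therapy regimen between Visit 1 (randomization) to Visit 3 (week 6". No cause is attached to it. Protocol 14.4 repeats the endpoint and places it outside adverse-event reporting: "In addition to AEs, the proportion of subjects temporarily or permanently changing their assigned therapy will be summarized". Protocol 11.1 anticipates departures of every kind and keeps the participants concerned in follow-up, referring to "Subjects who for any reason modify their hypertonic saline or dornase alfa treatment such that it deviates from their assigned treatment regimen".

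SAP 3.2.4 says instead: "The number and percent of participants changing their assigned therapy due to an adverse event is summarized by intervention arm". It adds one narrower summary, of participants "changing their assigned therapy when directed by a physician because of an adverse event is also summarized". Table 4.10 has the same scope: its main participant-level row is "Number (%) of Participants changing therapy regimen due to AE", and the other is the physician-directed subset. Table 4.5 does the same for serious events. The summary of changes at the front of the SAP records, against 3.2.4 and Table 4.10 and dated 3/2021, that the protocol had prespecified the endpoint and that it is here taken to mean modifications due to an adverse event. The rationale given is clarification.

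**The concern.** Adding a cause to an endpoint that had none changes what is estimated. As the two documents now stand, the protocol promises one proportion and the SAP delivers a subset of it.

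Safety of discontinuing is the first secondary objective (Protocol 4.2), and both studies are open label. In that setting, a participant told to stop who goes back to the drug is direct evidence on how acceptable stopping is, whether or not an adverse event was recorded and linked. If only linked changes are counted, the tables can understate how often assignments were abandoned. The shortfall could also differ between arms, because reasons for restarting in STOP need not resemble reasons for stopping in KEEP.

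**Working it through.** The endpoint carries no sample size, power or alpha figure, so there is nothing of the plan's own to reproduce. The check has three parts.

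**1. Does any exhibit give the any-reason proportion by arm?**

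| SAP exhibit | Restricted to (S)AE? | What it gives |
|---|---|---|
| Table 4.5 | Yes, serious events | Participants changing because of an SAE, and the physician-directed subset |
| Table 4.10 | Yes | Participants changing because of an AE, and the physician-directed subset |
| Table 1.3 | No | Participants excluded from the per-protocol population for adherence below 70%, overall or in the last two weeks |
| Table 3.3 | No | Distribution of diary adherence, and counts at or above 70% |
| Table 3.6 | No | Odds of meeting both 70% criteria |
| Listing 12.1 | No | Individual violations and deviations, with no proportion by arm |

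None does.

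**2. Can the 70% adherence summaries stand in for it?** The inputs are the 42-day period with a ±3-day window for Visit 3 (Protocol Appendix 2), adherence = days on assignment ÷ days submitted × 100 (Table 3.3, note 1), and thresholds of at least 70% overall and in the last two weeks (SAP 2.4).

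- Overall, complete 42-day diary: 12 days off gives 30/42 = 71.4%, which passes; 13 days off gives 29/42 = 69.0%, which fails.
- At the window limits, the most that passes is 11 days off of 39 (28/39 = 71.8%) and 13 of 45 (32/45 = 71.1%).
- Last two weeks, 14 diary days: 4 off gives 10/14 = 71.4%, which passes; 5 off gives 9/14 = 64.3%, which fails.
- With only the minimum diary completion, 30 of 42 days, 9 reported days off still passes (21/30 = 70%), and the other 12 days are unknown.

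Two cases with a complete 42-day diary show the effect. A STOP participant who uses the drug for 12 days running within the first four weeks and then stops again scores 71.4% overall and 100% in the last two weeks, so passes both. A participant who switches permanently 5 days or more before Week 6 fails the last-two-weeks criterion and is picked up. The summaries therefore catch sustained late switches but can miss short or earlier temporary ones. The protocol endpoint expressly includes temporary changes.

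**3. How large could the gap be?** The documents give no rate of therapy change, so this is illustration only. Take about 200 per arm (Protocol 6.1), and assume that 5% to 20% change for any reason and that 25% to 75% of those changes are AE-driven.

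- Smallest gap: 200 × 0.05 × (1 − 0.75) = 2.5 participants per arm.
- Largest gap: 200 × 0.20 × (1 − 0.25) = 30 participants per arm.

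The width of that range shows that the size is unknown.

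**The case against.** Four points on the other side have force.

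- **The change is disclosed.** The SAP's change table states it, and Protocol 14.1 lets the SAP carry modifications. A reader might infer that an endpoint was quietly dropped; the documents do not support that. What stands is that clarification is not a reason for adding a cause restriction, and no other reason is given.
- **Non-AE changes do not vanish from the report.** A reader might infer that participants who restart or stop for other reasons appear nowhere. That is too strong. Longer departures lower the adherence figures in Table 3.3, can show in Tables 1.3 and 3.6, and may be listed in Listing 12.1, since Protocol 12 names failure to follow the randomized assignment as a violation. None of these gives the proportion who changed.
- **Most symptom-driven restarts should qualify as AE-linked.** Protocol 10.1 defines an adverse event broadly, covering any unfavorable symptom during participation whether or not related, and investigators ask at each visit. The remaining cases are mainly changes made out of worry or preference, or for convenience, and symptoms never reported to the site. Sites cannot see diary answers after Visit 1 (Protocol 9.1.11), so a restart reported only there could not be linked to an event.
- **A careless any-change count would mislead.** Randomization requires only 70% adherence during screening (Protocol 6.3.3), so missed days in KEEP may be ordinary behavior. Counting each one as a temporary change, and testing it against active restarts in STOP, would blur the signal. This is accepted, and it shapes the fix.

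The SAP also shows that AE-linked change alone is incomplete. For the lower lung function cohort (SAP 3.2.13) it defines non-adherence by three outcomes: the AE-related change and two below-70% adherence criteria.

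**Conclusion.** The point holds for the therapy-change endpoint. Followed as written, the SAP leaves the any-reason proportion in Protocol 5.2 and 14.4 unreported and substitutes a subset. Sustained late switches would still be visible through the last-two-weeks criterion; short or earlier temporary changes may not be. The day counts assume complete diaries unless stated otherwise.

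The number of participants affected cannot be derived, and the 2.5 to 30 per arm above rests on assumed rates. The documents therefore do not support a claim that the harm of stopping is understated by any particular amount. The primary non-inferiority analysis, its alpha and its power are not touched, and the AE tables remain valid for what they count. This is a reporting gap in a secondary safety endpoint that should be closed, but it does not threaten the trial's main conclusion.

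**What to change.** - Add a row by arm at the top of Table 4.10: number (%) of participants with any temporary or permanent change from assigned regimen, for any reason, from Visit 1 to Visit 3. Give the difference with the Newcombe-Wilson 95% CI the table already uses. Keep it descriptive: the protocol asks for a summary, and a p-value adds nothing needed.
- Keep the AE-driven and physician-directed rows as subsets of it.
- Carry over the description of a change already in Table 4.10 (restarting in STOP, stopping in KEEP) without the AE condition. Base it mainly on concomitant-medication start and stop dates.
- State a supporting diary rule in the SAP before the table is run, including what happens when diary and medication record disagree, so that isolated missed doses in KEEP are not counted as regimen changes.
- Reword the entry in the SAP's change table: the AE-only definition is a narrowing of a prespecified endpoint, and the reason should be given.

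The cost is a short definition and a little more programming. No new data are needed: Protocol 9.1.2 captures medication dates, Appendix 2 has medications reviewed at every contact through Week 6, and the diary is daily.
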